9.1.11.2 C-SSRS

The C-SSRS was developed by researchers at Columbia University as a tool to help systematically assess suicidal ideation and behavior in subjects during participation in a clinical study of centrally-acting drugs [32]. The C-SSRS is composed of 3 questions addressing suicidal

behavior and 5 questions addressing suicidal ideation, with subquestions assessing the severity. The tool is administered via an interview with the subject.

Two versions of the C-SSRS will be used in this study: the Screening/Baseline C-SSRS Lifetime (assessing lifetime and the past year separately) and the Since-Last-Visit C-SSRS.

9.1.12 Order of Psychiatric/Neurological Rating Scales/Assessments

At screening, it is recommended to administer the BNSS first, followed by the C-SSRS. These assessments should precede all other psychiatric and neurological assessments at screening. After these assessments, the PANSS and then the MINI should be administered. At all other visits, the PANSS should take precedence over all other psychiatric assessments, and the BNSS should be administered after the PANSS. Thereafter, the order of assessments is not defined, except for the requirement that the CGI-SCH-I and CGI-SCH-S are completed after completion of all other psychiatric assessments (with an exception for the BACS, which does not contribute to the CGI assessments). Efforts should be made to perform the BACS cognition testing at approximately the same time of day throughout the study (postbaseline assessments must be administered ±2 hours from the time of baseline assessment administration).

9.1.13 PK Measurements

9.1.13.1 PK Sample Collection

Serial blood samples (one 4 mL sample per scheduled time point) for measurement of TAK-831 plasma concentrations will be collected into chilled Vacutainers containing the anticoagulant dipotassium ethylenediaminetetraacetic acid (K₂EDTA), according to the Schedule of Study Procedures (Appendix A).

The actual date and time of each PK blood sample collection, time since last dose was administered, and time since last meal will be recorded on the source document and eCRF.

Instructions for sample collection, processing, and shipment are provided in the laboratory manual.

[figure not shown]
9.1.13.2 Bioanalytical Methods

[figure not shown]
Plasma concentrations of TAK-831 will be measured by a validated high-performance liquid chromatography (HPLC) with tandem mass spectrometry method.

9.1.13.3 *Population PK*

PK will be assessed via population PK analysis (see Section 13.1.4).

9.1.14

9.1.16 Procedures for Clinical Laboratory Samples

All samples will be collected in accordance with acceptable laboratory procedures. The maximum volume of blood at any single visit is approximately 39 mL (Visit 3), and the approximate total volume of blood for the study is 182 mL. Details of these procedures and required safety monitoring will be given in the laboratory manual.

Table 9.a Approximate Blood Volume

	Number of Samples Per Subject										
	Volume per Sample (mL)	Screening (Days -28 to -15) (Visit 1)	Placebo Run-in (Day -14) (Visit 2)	Baseline (Predose Day 1) (Visit 3)	Day 28 (Visit 6)	Day 42 (Visit 7)	Day 56 (Visit 8)	Day 70 (Visit 9)	Day 84/ET (Visit 10)	Safety Follow-up (Days 94 to 98) (Visit 11)	Total Volume (mL)
Sample											
HBsAg, anti-HCV	4	1									4
Hb1Ac	2	1									2
Serum chemistry ^a	6	1		1	1		1		1	1 ^b	36
Hematology	2	1		1	1		1		1	1 °	12
Antipsychotic medications ^e	4	1	1			1			1		16
PK (TAK-831)	4			1	2	1	1		1		24
PD (D- and L-serine)	6		1	1	2	1	1		1		42
Total											182

Anti-HCV: antibody to hepatitis C virus; HBsAg: hepatitis B surface antigen; Hb1Ac: glycosylated hemoglobin; ET: early termination; PD: pharmacodynamics; PK: pharmacokinetics.

a Includes serum pregnancy test at the screening and safety follow-up visits and follicle-stimulating hormone (FSH) test at screening.

^b Serum chemistry tests will be performed at this visit only if clinically significant test results were reported at Day 84/ET. However, a serum pregnancy test must be performed for women of childbearing potential at this visit (blood sample volume will be reduced to 2 mL if other serum chemistry tests are not required).

^c Hematology will be performed at this visit only if clinically significant test results were reported at Day 84/ET.

^e Levels may be retested at investigator's request.

The tests that will be performed for each clinical laboratory sample are listed in Table 9.b.

Table 9.b Clinical Laboratory Tests

Hematology	Serum Chemistry	Urinalysis				
Hematocrit	Sodium	Specific gravity				
Hemoglobin	Potassium	pН				
RBC	Bicarbonate	Glucose				
Mean cell volume	Chloride	Protein				
Mean cell hemoglobin	Calcium	Occult blood				
Mean cell hemoglobin concentration	Magnesium	Microscopic battery (WBC,				
WBC with differential % and absolute	Phosphorus	RBC, epithelial cells, casts)				
(neutrophils, lymphocytes, monocytes,	Glucose					
eosinophils, basophils)	Blood urea nitrogen					
Platelets	Uric acid					
	Total cholesterol					
	Triglycerides					
	High-density lipoprotein cholesterol					
	Low-density lipoprotein cholesterol					
	Total protein					
	Albumin					
	Total bilirubin					
	Direct bilirubin					
	Alkaline phosphatase					
	ALT					
	AST					
	GGT					
	Creatine kinase					
	Amylase					
	Prolactin					
	Lactate dehydrogenase					
	Creatinine					
	Thyroid-stimulating hormone					
Other						
Serum	Urine					
HbA1c	Drug screen including: amphetamine, barbiturates, benzodiazepines,					
HBsAg and anti-HCV	cocaine, marijuana, methadone, methamphetamine, MDMA, opiates					
hCG (for pregnancy) ^a	(including oxycodone) and phencyclic	line				
FSH b	hCG (for pregnancy) ^a					
Antipsychotic medications ^c						

ALT: alanine aminotransferase; anti-HCV: antibody to hepatitis C virus; AST: aspartate aminotransferase; FSH: follicle-stimulating hormone; GGT: γ-glutamyl transferase; HbA1c: glycosylated hemoglobin; HBsAg: hepatitis B surface antigen; MDMA: 3,4-methylenedioxymethamphetamine; hCG: human chorionic gonadotropin; RBC: red blood cells; WBC: white blood cells.

^a Women of childbearing potential only. Serum hCG test to be performed at the screening and safety follow-up visits, and urine hCG test to be performed at all other scheduled time points. The hCG test can be repeated at any time at the investigator's discretion.

^b Postmenopausal females only.

^c For all antipsychotics for which an assay is available at the central laboratory.

The central laboratory will perform the hematology, serum chemistry, urinalysis, and other clinical laboratory tests. The results of laboratory tests will be returned to the investigator, who is responsible for reviewing and filing these results.

If subjects experience ALT or AST $>3 \times$ ULN, follow-up laboratory tests (at a minimum, serum alkaline phosphatase, ALT, AST, total bilirubin, GGT, and INR) should be performed within a maximum of 7 days and preferably within 48 to 72 hours after the abnormality was noted. (Refer to Section 7.6 and Section 10.2.3 for the appropriate guidance on reporting abnormal LFTs.)

If ALT or AST remains elevated >3× ULN on these 2 consecutive occasions, the investigator must contact the sponsor or designee for consideration of additional testing, close monitoring, possible discontinuation of study drug, discussion of the relevant subject details, and possible alternative etiologies. The abnormality should be recorded as an AE (please refer to Section 10.2.3).

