5.2.3 Safety Endpoints

- Percentage of subjects who experience at least 1 TEAE.
- Percentage of subjects who meet the markedly abnormal criteria for safety laboratory tests at least once postdose.
- Percentage of subjects who meet the markedly abnormal criteria for vital sign measurements at least once postdose.
- Percentage of subjects who meet the markedly abnormal criteria for safety ECG parameters at least once postdose.
- Percentage of subjects with treatment-emergent suicidal ideation or suicidal behavior as measured using the C-SSRS.

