 - When approval is given for a subject to miss an in-person study visit, a study site physician will speak directly with the subject by telephone or other medium (e.g. a computer-based video communication) during each visit window to assess subject safety and overall clinical status.
 - The study site physician or other qualified site personnel should conduct the following assessments within specified-visit window timeframes: AE assessments, documentation of concomitant medication, administration of C-SSRS, and an assessment of clinical symptoms.
 - Other study assessments may be collected using an alternative method as feasible, and may involve audio or video recording where allowed by local regulation. In some cases, audio and/or video recording of subject interviews may not be

possible and thus will deviate from the planned rater monitoring plan. This will be documented in the study records.

- In some instances sites may need to split visits or sites may only be able to perform a few procedures on site and some procedures may need to be performed remotely. Sites should inform sponsor or designee when this occurs.
- Sites may seek approval to extend a visit window in order to conduct an on-site visit. Assessments that cannot be completed during the protocol-specified window or within the visit window granted by the sponsor or designee will be considered missing data and such departures will be recorded in the study records.
- There will be no interval longer than 8 weeks between visits at which clinical laboratory tests are performed and vital signs are measured. Should this 8 week interval be reached for a particular subject, the site should reach out to the sponsor or designee to discuss withdrawal of the subject.
- Study site personnel may dispense additional investigational medicinal product to subjects at a visit to allow for potentially longer intervals between visits than originally planned per protocol, or investigational medicinal product may be supplied to subjects via delivery by site personnel or by courier.

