- The final visit should be performed in person. When it is not possible for the subject to come to the study site and the protocol specified visit window cannot be extended further, the preferred alternative for the final visit is for qualified study site personnel or designated clinical personnel to go to the subject's residence and conduct the protocol-specified procedures in that location. Assessments collected at a subject's residence should comply with applicable local regulations. If neither option is available with sponsor or designee approval, sites may conduct final visit procedures remotely as is feasible.

All subject discontinuations and alternative approaches to study procedures (ie, procedures not conducted per the Schedule of Procedures) due to the COVID-19 pandemic must be documented in the study records as related to COVID-19. Data collected using alternative methods may be handled differently in the final data analyses. This will be documented in the statistical analysis plan (SAP).

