- b Randomization is performed at Day 1 (Visit 3). If courier-related delays of laboratory test results occur (eg, due to COVID-19 related factors), Visit 3 may be delayed up to a maximum of 7 days after discussion with and approval from the sponsor or designee. For the screening and Day 1 visits, the study assessments may be conducted over 2 days that must be completed within a 5-day period or less. All Day 1 procedures must be completed and compared with the relevant study entry criteria prior to randomization. The first dose of study drug will be administered in the clinic at the end of the Day 1 visit (or as the last procedure if the Day 1 visit is split over 2 days). Subjects will then take study drug QD in the morning from Day 2 onward during the double-blind treatment period. Study procedures for the Day 84/ET (Visit 10) may be conducted over 2 consecutive days for subject's comfort and assessment feasibility. The final visit (Day 84/ET) should be performed in person. Alternative methods for administering study assessments may be considered when it is not possible for the subject to come to the study site or for the site staff or designated clinical personnel to go to the subject's residence for the final visit (Day 84/ET) in cases where unavoidable circumstance such as the COVID-19 pandemic are prohibitive. Investigators should contact the sponsor or designee to discuss individual subject circumstances (Section 9.1.1).
- For subjects who prematurely discontinue the study, the PANSS, BNSS, BACS, SCoRS, CGI-SCH-I, CGI-SCH-S, and assessments should be performed only in subjects who received at least 1 dose of study drug and are assessed within 1 week of the last dose of study drug; all other ET procedures should be performed for subjects who are assessed >1 week after the last dose of study drug.
- ^d If the date of a subject visit does not conform to the study plan, the timing of the subsequent visits should be planned to maintain the visit schedule relative to randomization.
- ^e In cases where antipsychotic serum levels are not available within the expected 7 days window, additional screening window may be granted in these cases with sponsor or designee approval.
- ^f May be obtained at screening (Visit 1) or placebo run-in (Visit 2) or at the informant's location. The initial discussion with the informant may include an oral informed consent.

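### If a remote Day 84/ET visit yields no blood samples, nothing can trigger the Visit 11 laboratory tests, so the protocol requires no end-of-study laboratory check

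*Protocol*

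**What the plan says.** **Visit 11 tests.** Protocol Section 9.1.16, Table 9.a, footnote b on chemistry: "Serum chemistry tests will be performed at this visit only if clinically significant test results were reported at Day 84/ET". Footnote c on hematology: "Hematology will be performed at this visit only if clinically significant test results were reported at Day 84/ET". The one unconditional blood test at Visit 11 is for pregnancy: "a serum pregnancy test must be performed for women of childbearing potential at this visit".

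**Remote final visit.** Section 9.1.1 wants the final visit in person at the site. The next choice is a visit to the subject's home. After that: "If neither option is available with sponsor or designee approval, sites may conduct final visit procedures remotely as is feasible". Footnote b of Appendix A applies the same order of preference to the combined Day 84/ET visit.

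**Assessments not done.** Under Section 9.1.1, an assessment not completed within the protocol window, or within an extension granted by the sponsor, "will be considered missing data and such departures will be recorded in the study records". No later make-up is asked for.

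**Interval limit.** Section 9.1.1 also states: "There will be no interval longer than 8 weeks between visits at which clinical laboratory tests are performed and vital signs are measured". When the limit is reached, the site is to discuss withdrawal of the subject with the sponsor or designee.

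**Schedule.** Appendix A places clinical laboratory tests at screening and on Days 1, 28, 56 and 84/ET, and the 12-lead ECG at screening, Day 1 and Day 84/ET. Neither row has an entry at Visit 11.

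**The concern.** The Visit 11 footnotes were written for a subject who was tested at Day 84/ET, and for that subject they are sensible: repeat the tests if something was found, otherwise stop. Amendment 04 then added a route by which Day 84/ET can pass with no samples. Read literally, the footnotes give an untested subject the same instruction as a subject tested with nothing significant found.

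What is at stake is individual safety. An abnormality that arose after the last laboratory set and persists at follow-up could go unseen although the subject is at the clinic for Visit 11. The ECG has a related gap, because Day 84/ET is its only scheduled postdose recording.

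**Working it through.** The plan states no figure to reproduce. The check is of logic and day counts.

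**1. The trigger.** There are three possible states at Day 84/ET:

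| Day 84/ET laboratory status | Visit 11 chemistry and hematology |
|---|---|
| Tested, clinically significant result | Required |
| Tested, no clinically significant result | Not required |
| Not tested | Not required: no result exists to meet the condition |

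The third row is the gap. It applies equally to a completer and to an early terminator, because Visit 10 is a single Day 84/ET visit under the same remote-visit rule.

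**2. Does the 8-week limit close it?** Inputs from Appendix A are Day 56 ±2, Day 84 ±5, and Visit 11 at 10 to 14 days after the last dose, ±2. Assume that Day 56 tests were done, that the last dose is on the day of the final visit, and that no window is extended.

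- Limit reached: 56 + 56 = Day 112; within windows 54 + 56 = Day 110 to 58 + 56 = Day 114.
- Visit 11: 84 + 10 = Day 94 to 84 + 14 = Day 98; latest in-window 89 + 14 + 2 = Day 105.
- Longest gap from the Day 56 tests to Visit 11: 105 − 54 = 51 days, which is under 56.

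For this subject the limit falls after the last visit. If the Day 56 tests were missed too, the limit is reached at 28 + 56 = Day 84, but the stated action is a discussion of withdrawal and no test is ordered. The limit does not mention ECG.

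**3. What the completer loses.** Scheduled postdose laboratory sets fall from 3 (Days 28, 56, 84) to 2. The time from last tests to final visit is 84 − 56 = 28 days (79 − 58 = 21 to 89 − 54 = 35 within windows). Scheduled postdose ECGs fall from 1 to 0.

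**4. What remains required at Visit 11.** Vital signs, the C-SSRS, adverse event assessment, and serum hCG for women of childbearing potential. Follow-up of abnormalities already known also continues under Section 10.2.1.2.

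**5. Blood volume.** Table 9.a counts six chemistry samples (6 × 6 mL = 36 mL) and six hematology samples (6 × 2 mL = 12 mL), and both totals include Visit 11. A Visit 11 draw is 6 + 2 = 8 mL and is already in the stated volumes.

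**6. How the SAP would use Visit 11 values.** SAP 7.12.2 keeps laboratory values taken more than 3 days after the last dose out of the descriptive tables, but takes all observations into the markedly abnormal evaluation. Visit 11 laboratory tests done under the present footnotes are already handled this way. SAP 7.12.4 has matching rules for ECGs, with a different consequence. For a subject with no other postdose ECG, a recording 10 to 14 days off drug would alone decide that subject's contribution to the endpoint: "Percentage of subjects who meet the markedly abnormal criteria for safety ECG parameters at least once postdose".

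**The case against.** The best case against is that this is a rare contingency. A remote final visit needs sponsor or designee approval, and comes only after a site visit, a further window extension and a home visit have all been ruled out. Visits may also be split, so remote ratings need not mean that no blood is drawn. The footnotes describe routine sampling and do not forbid more; the SAP expects unscheduled observations. Section 9.1.16 also defers details of safety monitoring to a laboratory manual that is not among the documents. All of this stands and limits the size of the point. It does not remove the gap, since none of the protocol text requires the tests and the footnotes as worded point the other way.

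Four stronger readings are tempting and are not supported:

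- *Early terminators are better protected than completers.* A reader might infer this from Appendix A footnote c: "all other ET procedures should be performed for subjects who are assessed >1 week after the last dose of study drug". That footnote sorts procedures by time since last dose. It does not address remote visits, and a remote ET visit leaves the same gap. The dividing line is in-person against remote.
- *A third of treatment goes unmonitored.* The arithmetic is right (28/84 = 33%), but 28 days is also the planned spacing of the laboratory tests, and the sponsor accepted gaps of up to 8 weeks.
- *A known renal signal would be missed.* Section 4.3 says that creatinine will go on being measured. It also describes the rat kidney finding as not adverse and species-specific, and reports no raised creatinine in the clinical studies it summarizes.
- *A Visit 11 ECG would repair the ECG endpoint.* An off-drug recording says little about effects on treatment. A normal one would count the subject as a postdose non-case beside subjects recorded at end of treatment.

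**Conclusion.** The point holds as a narrow gap in safety follow-up. When the Day 84/ET visit is remote and no samples are taken, the condition for Visit 11 chemistry and hematology cannot be met, and the protocol requires no end-of-study laboratory check even from a subject who attends Visit 11 in person. For a completer tested on Day 56, the 8-week limit falls at least 110 − 105 = 5 days after the latest in-window Visit 11.

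The day counts rest on Day 56 tests having been done, the last dose falling on the final-visit day, and no extension of the final visit beyond ±5 days. The conclusion also assumes that the laboratory manual does not already order the missed tests. The number of affected subjects is not given and is probably small. No primary or secondary efficacy conclusion changes. The correction is worth making because it is specific and costs very little.

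**What to change.** **Laboratory tests.** In Table 9.a, footnotes b and c, keep the present condition and add a second: *or if Day 84/ET tests were not obtained*. The results are an end-of-study safety check at 10 to 14 days off drug and do not stand in for late-treatment values. They follow the existing SAP 7.12.2 rules, so the laboratory section of the SAP needs no change.

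**ECG (optional).** In Appendix A, add a Visit 11 12-lead ECG when no Day 84/ET ECG was recorded, as an individual off-drug check. If this is adopted, flag it in SAP 7.12.4 so that the recording is listed but not treated as an on-treatment value in the postdose ECG endpoint. State also whether it enters the shift tables, which are defined by post-baseline visit.

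**Cost.** Two footnote edits and, per affected subject, one 8 mL draw at a visit already scheduled. The ECG option adds one schedule entry, one SAP sentence and one recording per affected subject. Nothing is gained if Visit 11 is also remote.

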9.1.16.1 Antipsychotic Plasma Levels

Experience with therapeutic blood monitoring of antipsychotic medications in clinical settings has demonstrated that a single antipsychotic plasma assessment may not be reliably representative of adherence to antipsychotic medications, so repeat testing may be warranted to confirm an initial finding of a lower than adequate plasma level.

Screening antipsychotic plasma levels that do not meet the criteria listed in the Antipsychotic Reference document should be repeated as soon as possible if, in the judgment of the investigator, the subject may actually be adherent to their medication regimen. Importantly, if the investigator's initial assessment results in a determination that the subject is most likely not being adherent with their antipsychotic medication regimen, the plasma level should not be repeated and the subject should be a screen failure.

If it is uncertain whether the subject is being adherent with treatment, it is recommended that antipsychotic plasma levels be urgently collected and sent to the central laboratory while the investigator collects additional information. If the investigator subsequently determines that the subject is not adherent to their medication regimen, the subject should be a screen failure.

It is important to note that Visit 2 should not be conducted before receipt of the antipsychotic plasma level indicating an acceptable value (in addition to the sponsor or designee and centralized eligibility vendor approvals). The Antipsychotic Reference document should be consulted for additional guidance in the management and interpretation of antipsychotic plasma level assays.

